522 (gender, age, ethnicity), duration of diabetes, comorbid conditions, medications, BMI, screening
523 labs, QOL assessment scores, appetite score, three-day food records analyzed using Nutrition
524 Database System for Research (NDSR) and physical activity questionnaire (IPAQ).⁴⁸ Follow up
525 data will include medications, BMI, body measurements, follow-up labs, QOL assessment
526 scores, appetite score, three-day food record, IPAQ, and adverse events.
527
528

529 **V. ETHICS:**

530 **A. INFORMED CONSENT**

531 After identification of eligible patients these individuals will be provided basic information
532 regarding the study and, if interested, a member of the research staff using inclusion/exclusion
533 criteria delineated elsewhere in the protocol will then screen patients. Informed consent will be
534 obtained before any trial related procedures including screening procedures. The consent form,
535 potential risks and benefits, and the rights of research participants will be explained to the
536 participant by the investigators or research coordinator. Individuals will be asked if they have
537 questions, and a member of the research staff will answer questions. The principal investigator
538 (PI) will also be available at all times to answer questions that participants may have during the
539 consent procedure or during the time a participant is enrolled in the study. The consent form will
540 be completed only by trained research personnel familiar with the study protocol procedures,
541 informed consent process, who have undergone CITI training in accordance with the IRB
542 guidelines of Emory University. A signed copy of the consent form will be provided to the
543 participant and a copy will be placed in the file that is maintained for each participant in the
544 study office. Adults who speak any of the following languages (English, Spanish) will be
545 approached for participation in the study.
546
547

548 **B. RECRUITMENT AND RANDOMIZATION**

549 Subjects will be recruited from the Diabetes Clinic at Grady Memorial Hospital and Emory
550 Healthcare clinics. Patients with diabetes will be identified electronically. Once a potential
551 candidate is identified, we will approach the primary clinician as well as the patient for consent.

552

553 Patients will be randomized consecutively using a computer-generated randomization table
554 provided by [name] at the Emory School of Public Health.

555

556

557 **VI. LIABILITY AND SUBJECT INSURANCE:**

558 **A. FINANCIAL OBLIGATION**

559 No additional cost to patients or to the institution will be incurred for research purposes. Patients
560 will not be billed for the laboratory work or any test that is being done only for study purposes.
561 Patients will be responsible for the cost of their usual ongoing medical care, including
562 procedures and/or non-study medications that their doctor requires as part of their usual medical
563 care.

564

565 **B. PAYMENT FOR PARTICIPATION**

566 Participation in this study is voluntary. Patients will receive \$25 for the screening visit, \$75 for
567 the enrollment visit, \$30 for the 1 month, 3 month, 6 month, 9 month and 12 month visit to
568 compensate for time and effort. Total compensation will be two hundred and fifty dollars
569 (\$250.00).

570

571 **C. RESEARCH INJURIES**

572 If a patient is injured because of taking part in this study, [name] and investigators at each
573 institution, along with the medical facilities will make medical care available. Emory University,
574 however, has not set aside any money to pay participants or to pay for their medical treatment.
575 The only exception is if it is proved that the injury or illness is directly caused by the negligence
576 of an Emory/Grady employee. "Negligence" is the failure to follow a standard duty of care.
577 Financial compensation for such things as lost wages, disability or discomfort due to an injury
578 related to the study is not available.

579

580

581 **VII. REFERENCES**

582

- 583 1. Ogden CL CM, Fryar CD, Flegal KM. . Prevalence of obesity among adults and youth:
584 United States, 2011–2014. NCHS data brief, no 219. *Hyattsville, MD: National Center
585 for Health Statistics 2015.*
- 586 2. Centers for Disease Control and Prevention. National Diabetes Statistics Report A, GA:
587 Centers for Disease Control and Prevention, US Department of Health and Human
588 Services; 2017.
- 589 3. Baum A, Scarpa J, Bruzelius E, Tamler R, Basu S, Faghmous J. Targeting weight loss
590 interventions to reduce cardiovascular complications of type 2 diabetes: a machine
591 learning-based post-hoc analysis of heterogeneous treatment effects in the Look AHEAD
592 trial. *Lancet Diabetes Endocrinol.* 2017;5(10):808-815.
- 593 4. Hamdy O, Mottalib A, Morsi A, et al. Long-term effect of intensive lifestyle intervention

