147 5.6% total body weight, with 22.7% excess BMI lost [delta BMI/(initial BMI-25)] over the 3-
148 month monitoring period. Participants reported decreases in appetite following the procedure at
149 all time points, with 15.8% reporting “somewhat less appetite”, 68.4% reporting “much less
150 appetite”, and 10.5% reporting “very much less appetite.”⁴³

151

152 In addition to weight loss, we anticipate that the cryovagotomy procedure will result in
153 significant improvement in glycemic control and cardiovascular risk factors, which may result in
154 long-term benefit is reducing diabetic complications. We propose a prospective, randomized
155 controlled trial to determine if a minimally invasive cryoablation procedure of the vagus nerve
156 will lead to greater weight loss and improvements in glycemic control, metabolic profile, and
157 cardiovascular risk factors compared to lifestyle intervention in obese patients with T2D. Our
158 data will provide preliminary data to support application for an NIH grant to further investigate
159 manipulation of the gut-brain axis for management of type 2 diabetes and obesity.

160

161 **III. DESCRIPTION OF STUDY PROTOCOL**

162

A. SPECIFIC OBJECTIVES:

163 **Objective 1. To compare glycemic control of patients undergoing vagus nerve cryoablation**
164 **plus lifestyle intervention at 6 and 12 months compared to lifestyle intervention alone in**
165 **obese patients with T2D.** Patients with T2D, BMI 30-40 kg/m², A1c 7.5-10.5% on stable doses
166 of oral antidiabetic agents will be randomized to cryoablation plus lifestyle or lifestyle
167 intervention alone and will be followed prospectively for 12 months in a controlled randomized
168 trial. We will compare changes in A1c levels between groups at 3, 6 and 12-months of follow up.
169

170 **Objective 2. To determine changes in weight and anthropometric metrics among patients**
171 **receiving cryoablation plus lifestyle intervention versus lifestyle intervention only.** Changes
172 in body weight, BMI, waist circumference, and BIA measured at baseline, 3 and 6 months after
173 intervention will be assessed.

174
175 **Objective 3. To determine safety of the cryoablation of the vagus nerve.** We will monitor
176 rates of AEs and SAEs related to the procedure which develop during the duration of the trial.
177

178 **B. ENDPOINTS:**

179 The primary endpoint of the trial is difference in glycemic control, defined as A1c, fasting

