180 glucose and insulin sensitivity (HOMA-IR), at 3, 6 and 12 months between the vagus nerve
181 cryoablation group and the lifestyle intervention monotherapy group.
182

183 The primary safety endpoint of the trial is occurrence of death and all procedure related
184 complications, such as bleeding, infection, pneumothorax, hemothorax, pulmonary injury,
185 complications of sedation, pain requiring hospital admission or treatment, dysphagia,
186 gastroparesis, nausea and vomiting, and gastrointestinal ulceration for the duration of the study.
187

188 Secondary outcomes include differences between treatment groups in any of the following
189 measures:

- 190 1. Body mass index (BMI), waist circumference, and waist-to-hip ratio at 3 and 6 months
191 compared to baseline
- 192 2. Lipids (total cholesterol, LDL, triglycerides) at 6 months compared to baseline
- 193 3. Systolic and diastolic blood pressure at 3 and 6 months compared to baseline
- 194 4. Daily caloric intake as measured by 3-day food recall compared to baseline at 3 and 6
195 months.
- 196 5. Changes in antihyperglycemic medication regimen compared to baseline at 3 and 6
197 months.
- 198 6. Appetite, hunger and satiety scoring by visual analog scale at baseline, 1 week, 1 month,
199 3 months and 6 months
- 200 7. Physical activity questionnaire (IPAQ) at baseline, 3 and 6 months
- 201 8. Fasting glucose and insulin levels at 3 and 6 months compared to baseline

202 203 **C. STUDY DESIGN:**

204 This is a randomized, controlled, unblinded clinical study in obese adult patients with T2D,
205 HbA1c 7.5-10.5%, BMI 30-40 kg/m² treated with non-insulin antidiabetic medications with

207 stable doses for at least 3 months.

208 Subjects will be pre-screened with the relevant questions from the Three Factor Food
209 Questionnaire by phone or in person to determine eligibility prior to consent. Following consent
210 and screening for trial eligibility, subjects will be randomized to treatment group. The primary
211 endpoint, glycemic control, will be assessed at 6 months post-procedure. Patients will be
212 recruited from the diabetes clinic at Grady Memorial Hospital and Emory University Clinics.
213

[figure not shown]
214 We will be screen up to 40 participants to be able to randomized 30 patients, they will be
215 enrolled in this pilot exploratory study. Patients will be randomly allocated to undergo either CT

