21. History of autonomic dysfunction, including amyloidosis, Parkinson's disease, autoimmune disease, spinal cord injury

G. STATISTICAL CONSIDERATIONS:

464 The primary outcome is the difference in glycemic control (as measured by HbA1c) at 6 and 12
465 months between the vagus nerve cryoablation group and the lifestyle intervention group.
466 Summary statistics including mean, median, and standard deviations for the changes in HbA1c
467 at 3, 6, 9 and 12 months will be computed. We will then compare the changes at 6 months
468 between the two treatment groups by a nonparametric Wilcoxon test or a two-sample t-tests
469 (with appropriate data transformation if needed). We will conduct one-way ANOVA to estimate
470 the mean difference in glycemic parameters at 6 and 12 months month between the two
471 treatment groups. We may further adjust for some important confounders by using linear
472 regression models. We will also assess the glycemic control outcomes simultaneously across
473 different follow-up visits (i.e. 12, 24 weeks) through repeated measures ANOVA models, which
474 appropriately account for within-subject correlations in the measurements. In addition, we will
475 consider repeated measures linear regression model with visits incorporated as a continuous time
476 variable. We may include other covariates in the model when feasible.

477 The primary safety endpoint of the trial is the occurrence of death and all procedure related
478 complications, such as bleeding, infection, pneumothorax, hemothorax, pulmonary injury,
479 complications of sedation, pain requiring hospital admission or treatment, dysphagia,
480 gastroparesis, nausea and vomiting, and gastrointestinal ulceration for the duration of the study.
481 We will first use the Chi-square test (or Fisher's exact test) to compare the occurrence of this
482 primary safety endpoint between the two treatment groups. We will perform logistic regression
483 to evaluate the group difference while adjusting for other potential confounders such as age,
484 gender, and BMI. In addition, we will compare the number of procedure related complications
485 by using Poisson regression or Negative Binomial regression between the two treatment groups.
486 Standard model selection (e.g. forward, backward variable selection) and model checking
487 procedures (e.g. deviance residual plot and Hosmer- Lemeshow test) will be performed to ensure
488 the adequacy of the final models.

489

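### Sections III.B and III.G define the primary efficacy endpoint differently, and neither the testing rules nor the power sentence settles which result is primary

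*Combined protocol and SAP*

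**What the plan says.** Two sections of the combined protocol and SAP give a full definition of the primary efficacy endpoint.

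- Section III.B (Endpoints): "The primary endpoint of the trial is difference in glycemic control, defined as A1c, fasting" and, continuing on the next line, "glucose and insulin sensitivity (HOMA-IR), at 3, 6 and 12 months between the vagus nerve" cryoablation and lifestyle groups.
- Section III.G (Statistical Considerations): "The primary outcome is the difference in glycemic control (as measured by HbA1c) at 6 and 12" months.

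Section III.C (Study Design) uses the primary label as well, but gives only a time: "endpoint, glycemic control, will be assessed at 6 months post-procedure". It does not say which measure stands for glycemic control.

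The neighbouring text does not resolve the difference.

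- The heading of Objective 1 in III.A reads "plus lifestyle intervention at 6 and 12 months compared to lifestyle intervention alone in" the target population, while the text beneath it adds a 3-month comparison.
- Secondary outcome 8 in III.B lists fasting glucose at 3 and 6 months, which the same section has already made primary.
- III.G summarises HbA1c "at 3, 6, 9 and 12 months will be computed. We will then compare the changes at 6 months", so its first between-group test is at 6 months. That test is made "between the two treatment groups by a nonparametric Wilcoxon test or a two-sample t-tests", with no rule for choosing between the two.
- The repeated-measures analysis in III.G covers "different follow-up visits (i.e. 12, 24 weeks) through repeated measures ANOVA models, which" account for within-subject correlation. Those visits end at 24 weeks, although the same section makes 12 months primary.

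No significance level, sidedness, testing order or success rule appears anywhere. The sample size paragraph claims 80% power with 12 patients per group for a change of 1.2 SD in an unnamed glycemic control outcome.

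**The concern.** A reader cannot tell from the plan which single result will be reported as the primary one. Under III.B there are nine candidates and under III.G two. The Wilcoxon-or-t-test choice adds a further option to each.

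This matters because III.D states that participants and study staff know the treatment arm. With the definition open, the measure, visit and test could be settled after outcomes have been seen by arm, and nothing in the document would show that this had happened. III.B's own overlap makes it concrete: a 3- or 6-month fasting glucose result could be presented as primary or as secondary, with text to support either.

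The results are meant to support a grant application (Section II) and the planning of larger randomized studies (sample size paragraph), so it matters which estimate is carried forward as the main one.

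**Working it through.** **1. Count the comparisons under each primary statement.**

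| Section | Measures | Visits (months) | Comparisons |
|---|---|---|---|
| III.B | A1c, fasting glucose, HOMA-IR | 3, 6, 12 | 3 × 3 = 9 |
| III.G | HbA1c | 6, 12 | 1 × 2 = 2 |
| III.C | not named | 6 | not determined |

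HbA1c at 6 months is the only cell that lies in both full definitions and at the III.C visit.

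**2. Reproduce the stated power.** Inputs from the sample size paragraph: 15 per group, 20% attrition, difference 1.2 SD. Evaluable per group: 15 × 0.8 = 12. Assumption, because the documents give neither: two-sided alpha 0.05.

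Two-sample t-test: degrees of freedom 2 × 12 − 2 = 22; noncentrality 1.2 × √(12/2) = 2.94. The noncentral t distribution gives power of **80.2%**, and the difference detectable with exactly 80% power is 1.197 SD. The plan's figure is reproduced. One-sided 0.05 would give 88.5%, so two-sided 0.05 is the level that fits. An exact Wilcoxon test on normal data has about 76% power (100,000 simulations), so the choice of test has a small effect on the claim.

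The 80.2% holds for any one comparison tested unadjusted, and for the first test in a fixed sequence. It does not identify which comparison was meant.

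**3. Illustrate what the missing success rule could cost.** Suppose each comparison is tested at two-sided 0.05 without adjustment and any one significant result counts as success. If the tests were independent, the chance of at least one false positive would be 1 − 0.95^k: 1 − 0.95² = 9.75% for two and 1 − 0.95⁹ = 37.0% for nine. Repeated glycemic measures on the same patients will be correlated, so the more useful figures come from simulation (12 per group, t-tests, 200,000 runs, an assumed common correlation):

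| Correlation | Two comparisons | Nine comparisons |
|---|---|---|
| 0.3 | 9.6% | 33.1% |
| 0.5 | 9.2% | 27.4% |
| 0.7 | 8.4% | 21.0% |
| 0.9 | 7.1% | 12.7% |

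The plan neither states nor excludes this rule. The table shows what is left open, not what the trial's error rate is.

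**The case against.** The best defence is that the intended primary is easy to guess. The hypothesis in Section I concerns 6 months, III.C says 6 months, and the first test in III.G is on the 6-month HbA1c change. The study calls itself a pilot exploratory study of 30 patients, for which strict error control is not expected. Both points stand and they lower the severity. They do not remove the contradiction: no sentence designates HbA1c at 6 months as the sole primary, and III.B and III.G each say something wider.

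Three stronger readings are tempting and are not supported.

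- **That the 80% power is wrong, or valid only if there is a single comparison.** With a Bonferroni adjustment, power per comparison would fall to 70.1% for two and 46.5% for nine. But the plan states no adjustment, and these figures are not the power of the whole procedure. Power for at least one Bonferroni-adjusted success, with 1.2 SD true on every comparison, is about 88% to 77% for two and 95% to 67% for nine at correlations of 0.3 to 0.9. Nor does the plan require all comparisons to succeed. The power sentence can be read as a per-outcome statement, and on that reading it is correct.
- **That there are three rival definitions.** III.C names no measure, and its visit lies inside both of the others. The conflict is between III.B and III.G.
- **That 12-month HbA1c may not be collected**, because one sentence in III.C places blood work at baseline, 3 and 6 months only. The same section provides for assessing glycemic control at every visit, and its laboratory table includes HbA1c at 12 months. Collection is clear; only the status of the 12-month result is not.

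**Conclusion.** The concern holds in this form: III.B and III.G contradict each other on the primary measure and visits. Fasting glucose at 3 and 6 months is both primary and secondary, and the repeated-measures visits stop short of a time point called primary. The alpha, sidedness, testing order and success rule are absent, and the power sentence is attached to no measure or visit.

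The 80% figure is not an arithmetic error. It is reproduced at 80.2% under an assumed two-sided 0.05. The false-positive range of about 7–10% for two comparisons and 13–33% for nine depends on an any-one-counts rule that the plan does not state and on assumed correlations of 0.9 to 0.3, so the finding does not rest on it. It rests on the text.

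This should be corrected before outcomes are analysed. For a self-described pilot whose natural reading is HbA1c at 6 months, it is not a defect that stands in the way of the trial.

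**What to change.** - In III.A, III.B, III.C and III.G, name the same single primary endpoint. Suggested: the between-group difference in HbA1c change from baseline to 6 months, which agrees with the Section I hypothesis, III.C and the first test in III.G.
- Pre-specify one test at two-sided 0.05 and attach the 80% sentence to that endpoint and test. A two-sample t-test reproduces the figure; if Wilcoxon is chosen, restate the power.
- Make fasting glucose, HOMA-IR and HbA1c at the other time points secondary, and list fasting glucose only there. HbA1c at 9 months is at present only summarised and may stay so.
- Extend the repeated-measures visits in III.G to 12 months.
- If the sponsor wishes to keep 12 months as primary, test it only after the 6-month test is significant. The 6-month test then keeps 80.2% power. Success at both has about 67–75% probability if 1.2 SD is true at each and the correlation is 0.3 to 0.9.
- Date the amendment before any comparison of outcomes by arm. If one has already been made, say so and report the result as exploratory.

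The cost is a wording amendment; sample size, visits and laboratory schedule do not change. The downside is that a positive 12-month, fasting glucose or HOMA-IR result could not alone be called the primary result.

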216 guided cryoablation of the vagus nerve plus lifestyle intervention or lifestyle intervention alone.

217 **Group 1:** CT guided cryoablation of the vagus nerve plus lifestyle intervention (n=15).

218 **Group 2:** Lifestyle intervention by trained RD/CDE (n=15).

219 All subjects will have the procedure performed at Grady Memorial Hospital or Emory University
220 Hospital Midtown or Johns Creek by trained study personnel.
221

222 The study schema is shown below. Both groups will undergo screening for eligibility followed
223 by randomization. If the subject is not fasting at time of initial consent and screening, he/she will
224 be brought back for a subsequent visit with fasting blood work. Subjects must be randomized
225 within 4 weeks of the screening visit. If the randomization visit falls outside of the 4 week time
226 frame, the subject must undergo repeat screening procedures. In- person lifestyle counseling will
227 be provided at baseline visit for both groups. Those undergoing cryoablation will receive a phone
228 call 24 hour post-procedure to evaluate for any immediate complications, 1 week in person
229 follow up visit, as well as a safety call at 2 months. Subjects in both groups will have weekly
230 contact with RD and in person follow up visits at 4 weeks, 3 months, and 6 months. Blood work,
231 anthropometric data and questionnaires will be administered at baseline, 3 months, and 6 months.
232 Safety follow up appointments will be scheduled at 9 months and 12 months, though no further
233 lifestyle counseling will be provided after 6 months. Questioning regarding adverse events and
234 side effects will occur at all visits, as well as assessment of glycemic control. Anti-
235 hyperglycemic medications will be adjusted at visits under the direction of the endocrinologist,
236 or as needed for clinically significant hypo- or hyperglycemic events.

237
238

239 Blood work will be as follows: For all lab parameters, subject results must be within the
240 reference range unless otherwise specified by inclusion/exclusion criteria or if assessed by study
241 physician to be not clinically significant.

Lab test	Baseline	3 months	6 months	9 months	12 months
Complete metabolic panel	X	X	X	X	X
Pregnancy test	X	X	X	X	
HbA1c	X	X	X	X	X
Lipid panel	X		X		
Insulin level	X	X	X		X
TSH	X				

242
243

D. STUDY PROCEDURE:

244 **Cryoablation procedure (to be performed by [name] or [name]):** Subjects will

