357 adjusted. Subjects on metformin will have the dose titrated to a maximum of 2000 mg/d if
358 tolerated. Sulfonylureas can be titrated to maximal doses per manufacturer instruction. Subjects
359 may be prescribed rescue therapy with insulin in the event of significant hyperglycemia
360 unresponsive to titration of oral agents. In the setting of BG <100 mg/dl, sulfonylurea doses will
361 be decreased by 50% and discontinued if necessary. If BG <55 mg/dl, sulfonylureas will be
362 stopped. Metformin will be stopped if hypoglycemia persists.

363

364 **Technical success rate of the procedure and procedure related complications:**
365 Discontinuation of the trial will occur if 3 participants within the first 8 of 30 planned experience
366 significant adverse events (AEs) (Grade 3 procedure-related AE or procedure-related serious
367 AE) at any point during follow-up and if 4 participants experience significant AEs (Grade 3
368 procedure-related serious AE) at any time. The trial will be stopped at any point if a Grade 4 or
369 Grade 5 AE occurs until determination can be made regarding its potential relationship to study
370 involvement.

371

372 **Grading of AEs:**

373

Grade 1	Mild; asymptomatic or mild symptoms; clinical or diagnostic observations only; intervention not indicated
Grade 2	Moderate; minimal, local or noninvasive intervention indicated; limiting age-appropriate instrumental ADL
Grade 3	Severe or medically significant but not immediately life-threatening; hospitalization or prolongation of hospitalization indicated; disabling; limiting self-care ADL
Grade 4	Life-threatening consequences; urgent intervention indicated
Grade 5	Death related to AE ⁶⁷

374

375 Specific clinical signs or symptoms that will qualify for the above criterial include (amongst
376 other potential Grade 3-5 AEs not listed here): constitutional symptoms (severe fatigue
377 interfering with ADLs, fever $> 40^{\circ}\text{C}$, prolonged and/or severe rigors), endocrine (uncontrolled
378 hyperglycemia, ketoacidosis), gastrointestinal (inadequate caloric intake requiring TPN or IV
379 fluids, diarrhea requiring IV fluids and/or manifesting as >7 stools/day, symptomatic abdominal
380 distention or bloating, severe abdominal pain requiring narcotics, ileus, severe nausea requiring
381 hospitalization, bowel obstruction or perforation), hemorrhage requiring intervention, infection
382 requiring antibiotics, or pain interfering with ADLs.

383

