417 months, with failed prior attempts at dietary interventions to optimize diabetes control
- 418 5. BMI 30-40 kg/m²

419 6. Willing to comply with study requirements
420 7. Documented negative pregnancy test in women of child bearing potential and use of an
421 effective birth control method
422 8. Average score of ≥ 3 on questions 4, 8, 9, 13, and14 from the Three Factor Eating
423 Questionnaire, to be assess prior to consent via phone screen or in person.

Exclusion criteria:

1. Diagnosis of type 1 diabetes or history of diabetic ketoacidosis
2. Use of insulin therapy
3. Significant kidney disease (eGFR < 60 ml/min/1.73m²)
4. Current drug or alcohol addiction
5. Thyroid disease unless underlying diagnosis is primary hypothyroidism on stable medications for >3 months with TSH in reference range at time of screening visit
6. Systemic steroid use within 30 days prior to randomization
7. Use of prescription or over the counter weight loss medications within 6 months prior to randomization
8. Weight gain/loss >5% over the past 6 months
9. Previous GI surgery or abnormal GI anatomy which may limit technical feasibility of the procedure
10. Recent diagnosis of cardiovascular disease requiring PCI or CABG within the past 6 months
11. Abnormal pathologies or conditions of the GI tract, including peptic ulcers, hiatal hernia, active gallbladder disease, pancreatitis, cirrhosis, inflammatory bowel disease, upper GI bleed within 6 months of randomization
12. Any condition or major illness that places the subject at undue risk by participating in the study
13. Psychiatric condition rendering the subject unable to understand the possible consequences of the study
14. Inability to provide informed consent
15. Female subjects who have been pregnant within 6 months or breast-feeding at time of enrollment into the study, or women who plan to become pregnant within the next 12 months
16. Diagnosis of anemia, RBC transfusion in the preceding 3 months or expectation to receive transfusion within the next 12 months, or hemoglobinopathies that would affect HbA1c reliability
17. Active or recent infection
18. Immunosuppression
19. History of coagulopathy or high risk for development of deep vein thrombosis (including congestive heart failure, those who are non-ambulatory, active leukemia/lymphoma, prior thrombotic events, family history of thrombosis)
20. History of blood pressure instability (systolic BP \leq 100 or \geq 160 mmHg)

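### HOMA-IR and fasting insulin are compared between arms with no rule for values taken after rescue insulin, which can include injected insulin

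*Combined protocol and SAP*

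**What the plan says.** All references are to the combined protocol and SAP.

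- **III.B Endpoints.** The primary endpoint is a between-arm difference in glycaemic control, made up of HbA1c and fasting "glucose and insulin sensitivity (HOMA-IR), at 3, 6 and 12 months between the vagus nerve" cryoablation group and the lifestyle group. Secondary outcome 8 is "Fasting glucose and insulin levels at 3 and 6 months compared to baseline".
- **III.C Study Design, laboratory table.** The row "Insulin level" is marked at baseline, 3, 6 and 12 months. No C-peptide is listed and the assay is not described.
- **III.F Study Subject Selection.** Exclusion criterion 2 is "Use of insulin therapy".
- **III.E Potential Risks and Benefits.** After entry, subjects "may be prescribed rescue therapy with insulin in the event of significant hyperglycemia" that has not responded to adjustment of oral agents. The provision is not limited to one arm. Sulfonylurea doses may also be raised, lowered or stopped.
- **III.G Statistical Considerations.** The primary outcome is here measured by HbA1c alone. One-way ANOVA is to estimate "the mean difference in glycemic parameters at 6 and 12 months month between the two" groups, and continuous secondary outcomes follow the primary plan. Covariates are optional and unnamed. The section does not mention rescue insulin and has no exclusion, missing-data or sensitivity rule for values taken after it.

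**The concern.** HOMA-IR is an index of insulin sensitivity only if the insulin measured is the patient's own. The entry criteria secure that at baseline; nothing secures it at follow-up. Once rescue insulin has started, a change from baseline can compare endogenous insulin with a mixture of endogenous and injected insulin.

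Randomisation does not protect against this, because rescue happens after randomisation and is triggered by the outcome domain under test. The trial is unblinded, and medication is adjusted at visits under the endocrinologist's direction. The number of rescued patients may therefore differ by arm, and the between-arm contrast in HOMA-IR or fasting insulin would carry that difference as bias.

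Making HOMA-IR secondary does not remove the problem, since fasting insulin is a listed outcome in its own right. The trial is also meant to supply preliminary data for larger randomised studies and a grant application, so a misleading insulin-sensitivity result could be carried forward.

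**Working it through.** **1. The plan's own figure.** III.G states 80% power for a difference of 1.2 SD with 12 evaluable patients per arm (15 × 0.8 = 12). A two-sample t-test with two-sided alpha 0.05 (assumed; no alpha is stated) has 22 degrees of freedom and noncentrality 1.2 / √(1/12 + 1/12) = 2.94. Power is 80.2%, so the figure reproduces. The point below concerns validity and does not depend on it.

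**2. Inputs for an illustration.** From the documents: 12 evaluable patients per arm, so each is 1/12 = 8% of an arm. Assumed, because the documents give no figure:
- k = 2 or 3 patients rescued, all in one arm
- measured fasting insulin multiplied by m = 2 or 3 in those patients
- HOMA-IR proportional to fasting insulin × fasting glucose
- fasting glucose falling by g = 20% or 40% under rescue insulin
- no true difference between arms

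**3. Shift in the arm's geometric mean.** Fasting insulin: m^(k/12) − 1. HOMA-IR: [m(1 − g)]^(k/12) − 1.

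| m | g | m(1 − g) | Insulin, k = 2 | HOMA-IR, k = 2 | Insulin, k = 3 | HOMA-IR, k = 3 |
|---|---|---|---|---|---|---|
| 2 | 40% | 1.2 | 12% | 3% | 19% | 5% |
| 2 | 20% | 1.6 | 12% | 8% | 19% | 12% |
| 3 | 40% | 1.8 | 20% | 10% | 32% | 16% |
| 3 | 20% | 2.4 | 20% | 16% | 32% | 24% |

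Fasting insulin shifts by 12-32%. HOMA-IR shifts by 3-16% with two rescued and 5-24% with three.

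**4. Direction.** With k₁ and k₀ rescued in the two arms, the between-arm ratio of fasting insulin is distorted by m^((k₁ − k₀)/12). It is 1 when the numbers are equal and reverses when the other arm is rescued more. If the assay does not detect the injected product and the patient's own insulin falls, m is below 1. With m = 0.5 (assumed), 0.5^(2/12) = 0.89 and 0.5^(3/12) = 0.84, so insulin reads 11-16% too low. A fall in glucose then adds to the HOMA-IR error instead of offsetting it.

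**5. Effect on the test.** In simulation with no true difference, 12 per arm, SD of change 0.5 on the log scale (assumed) and rescue in one arm only, the nominal 5% false-positive rate of the t-test becomes:
- k = 2: 6.5% (m = 2) or 8.2% (m = 3)
- k = 3: 9.5% (m = 2) or 14.0% (m = 3)
- k = 1: about 5% for either m

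These hold glucose fixed, so they apply to fasting insulin. For HOMA-IR with m above 1 and some glucose offset, the inflation is smaller.

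**6. Cost of setting values aside.** The same t-test at 1.2 SD gives 76.0% power with 12 vs 10 and 73.3% with 12 vs 9. The difference detectable with 80% power rises from 1.20 SD to 1.26 and 1.30 SD.

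**The case against.** The case for leaving the plan alone has real content.

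- **Rescue may be rare.** Oral doses are adjusted before insulin is considered, and its use is permissive. Two or three of 12, all in one arm, is a scenario and not a forecast. This stands, and it is why the figures are only illustrative.
- **Some rescued patients may leave the data.** III.E names uncontrolled hyperglycaemia among qualifying Grade 3-5 events, and subjects with such events are withdrawn. But rescue insulin is not itself a stated reason for withdrawal, and removal that depends on the outcome would be a selection problem of its own.
- **The inferential effect is modest.** At a log SD of 0.5, the 1.2 SD target is a ratio of exp(0.6) ≈ 1.8, well above the largest shift in the table. III.G also permits transformation or a Wilcoxon test, which limits the pull of a few extreme values. Neither makes the affected values valid.
- **HbA1c is the primary measure in III.G.** True, but HOMA-IR and fasting insulin are still compared between arms.
- **Setting values aside has its own bias.** It removes the worst-controlled patients, and it drops values taken after a short rescue has ended. This stands and is why the fix needs a sensitivity analysis. Sulfonylurea changes may also disturb fasting insulin, less strongly, and the fix does not deal with them.

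A reader might go further and infer that the artefact will favour cryoablation, because lifestyle-only patients would be rescued more and injected insulin would raise their readings. The documents do not support that: they give no rescue rate by arm and do not say what the assay detects. Nor do they state a decision to analyse all values alike; that is only what follows by default from a plan that is silent.

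**Conclusion.** The gap is real. The plan compares an insulin-sensitivity index and fasting insulin between arms, permits injected insulin during follow-up, and has no rule that separates the two. Post-rescue values do not validly measure insulin sensitivity, whichever way they are distorted. Bias between arms is possible because rescue depends on glycaemic control in an unblinded trial; its direction and size cannot be fixed from the documents.

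Under the stated assumptions the shift is 12-32% for fasting insulin and about 3-24% for HOMA-IR. It would be wrong to quote 12-32% for HOMA-IR as well, since that holds glucose constant although rescue insulin is given to lower it. The point does not touch the HbA1c comparison. It should be settled before any between-arm comparison of these measures.

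**What to change.** Leave the rescue rule as it is and add the following to III.G:

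1. Record the start and stop dates of rescue insulin. Section IV already collects follow-up medications.
2. Do not analyse HOMA-IR or fasting insulin as observed once rescue insulin has started. Treat those values as missing in a likelihood-based repeated-measures model on the log scale, which keeps each patient's earlier visits.
3. Report the number of values set aside by arm and visit.
4. Because this missingness depends on glycaemic control, add a sensitivity analysis that either includes the observed values or ranks rescued patients as worst.
5. List HOMA-IR as a secondary outcome, so that III.B agrees with III.G, where HbA1c measures the primary outcome.

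The cost is a few SAP sentences and two date fields, plus some lost values and power for HOMA-IR and fasting insulin only. The figures in step 6 of the working are for a complete-case comparison; the repeated-measures model may recover part of the loss from visits before rescue.
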